5.1.9 Cycle 2, Days 8 and 15 (Arm B only)

- Vital signs (heart rate, blood pressure, and respiratory rate)
- Weight
- Laboratory assessments
 - Hematology: hemoglobin, hematocrit, white blood cell count with differential, platelet count
 - Serum chemistry: sodium, potassium, chloride, bicarbonate, blood urea nitrogen, creatinine, glucose (random), total bilirubin, alkaline phosphatase, ALT, AST, albumin
 - Serum calcium, magnesium, phosphorus
- Ganetespib administration via silicone VADS

5.1.10 Cycle 3 Day 1, and Day 1 of Subsequent Cycles

- Clinic visit
- Record concomitant medications
- Vital signs (heart rate, blood pressure, and respiratory rate)
- Physical examination
- Weight (Arm B only)
- ECOG performance status
- Record AEs (using CTCAE v4 grading criteria)
- Laboratory assessments
 - Hematology: hemoglobin, hematocrit, white blood cell count with differential, platelet count

CONFIDENTIAL

This document is confidential. Do not disclose or use except as authorized.

- Serum chemistry: sodium, potassium, chloride, bicarbonate, blood urea nitrogen, creatinine, glucose (random), total bilirubin, alkaline phosphatase, ALT, AST, albumin
- Serum calcium, magnesium, phosphorus
- CEA, CA27-29, if elevated at baseline. In patients with elevated markers at baseline, tumor markers should subsequently be drawn once every 2 cycles.
- 12-lead ECG (Arms B and C only). If pre-dose QTc >470 ms a repeat ECG is required approximately 24 hours after the Ganetespib dose. See section 5.6 for additional ECG requirements for patient at moderate to high risk of torsades de pointes.
- Radiologic imaging studies to evaluate tumor status. Contrast computed tomography (CT) (or without contrast if contraindicated) of chest and abdomen is preferred. Magnetic resonance imaging (MRI) of chest and abdomen is an acceptable alternative. Note: PET-CT scans are *not allowed* per protocol for primary assessment of response. PET-CT scans may be done according to clinical judgment to supplement CT or MRI scans in cases where results of the PET-CT may clarify or resolve a clinical question.
- Measurements of palpable/visible lesions, if used as a target lesion (for example, chest wall nodule)
- Follow-up imaging and measurements should be done every 2 cycles (8 weeks) and every 2-4 cycles (8-16 weeks) for patients who have been on study for >1 year. Imaging can be done +/- 1 week from targeted date but before start of the subsequent cycle.

5.1.11 Days 8 and 15 of Cycle 3 and Subsequent Cycles (Arm B only)

- Vital signs (heart rate, blood pressure, and respiratory rate)
- Weight
- Laboratory assessments
 - Hematology: hemoglobin, hematocrit, white blood cell count with differential, platelet count
 - Serum chemistry: sodium, potassium, chloride, bicarbonate, blood urea nitrogen, creatinine, glucose (random), total bilirubin, alkaline phosphatase, ALT, AST, albumin
 - Serum calcium, magnesium, phosphorus
- Ganetespib administration via silicone VADS

5.1.12 Time of Crossover from Arm A to Arm C (applies only to patients initially randomized to Arm A)

- Clinic visit
- Vital signs (heart rate, blood pressure, and respiratory rate)
- Physical exam
- Weight
- ECOG performance status
- Record AEs (using CTCAE v4.0 grading criteria)
- Record concomitant medications

CONFIDENTIAL

This document is confidential. Do not disclose or use except as authorized.

- Laboratory assessments
 - Hematology: hemoglobin, hematocrit, white blood cell count with differential, platelet count
 - Serum chemistry: sodium, potassium, chloride, bicarbonate, blood urea nitrogen, creatinine, glucose (random), total bilirubin, alkaline phosphatase, ALT, AST, albumin
 - Serum calcium, magnesium, phosphorus
 - CEA, CA 27-29
- 12-lead ECG
- Research blood draw for CTCs, Streck tube, PBMCs. See section 9.5.
- Optional research biopsy. See section 9.5.
- Bone scan
- Measurements of palpable/visible lesions, if used as a target lesion (for example, chest wall nodule)
- Review of films by central radiology reviewer (DF/HCC Tumor Imaging Metrics Core) and confirmation of progression by overall study PI (REQUIRED before patient receives first dose of ganetespib)

5.1.13 Prior to Removal from Protocol Treatment (applies to Arms A, B, and C)

- Review of films by central radiology reviewer (DF/HCC Tumor Imaging Metrics Core) and confirmation of progression by overall study PI is REQUIRED for patient to be taken off protocol treatment in either arm, if off-treatment reason is progression.
- “Real-time” central review for progression is not required if the off-study reason is other than progression (i.e. for toxicity, etc.); however, central review will be performed at a later time in order to adjudicate the primary endpoint (PFS)

5.1.14 End of Protocol Treatment (within 30 days after the last dose of protocol treatment)

- Clinic visit
- Vital signs (heart rate, blood pressure, and respiratory rate)
- Physical exam
- Weight
- ECOG performance status
- Record AEs (using CTCAE v4.0 grading criteria)
- Laboratory assessments
 - Hematology: hemoglobin, hematocrit, white blood cell count with differential, platelet count
 - Serum chemistry: sodium, potassium, chloride, bicarbonate, blood urea nitrogen, creatinine, glucose (random), total bilirubin, alkaline phosphatase, ALT, AST, albumin
 - Serum calcium, magnesium, phosphorus
- Research blood draw for CTCs, PBMCs, and Streck tube. See section 9.5.
- Optional research biopsy. See section 9.5.

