6.2.1 Ganetespib

Dose Level	Dose	Route	Schedule	Cycle Length
Starting dose	200 mg/m ²	IV	D1, 8, 15	28 days
First dose reduction	175 mg/m ²	IV	D1, 8, 15	28 days
Second dose reduction	150 mg/m ²	IV	D1, 8, 15	28 days

As detailed in Sections 5.1 and 14.2, at the time of initial study design, it was decided that in the case of more than 2 DLTs within the first 10 patients on Dose Level 1 (starting dose 200 mg/m²), the study would close temporarily to accrual while the events were adjudicated. Based upon results of this adjudication, the study would re-open at Dose Level -1 (starting dose 175 mg/m²). In this event, there would be only 1 allowed dose reduction (i.e. to 150 mg/m²) for patients entered at this starting dose level. Once decreased, doses would NOT be re-escalated. This DLT rule was not triggered for the first 10 patients randomized to Arm B; therefore enrollment to Arm B has continued at Arm B Dose Level 1 and treatment on Arm C has continued at Arm B Dose Level 1.

If possible, symptoms should be managed symptomatically. In the case of toxicity, appropriate medical treatment should be used (including anti-emetics, anti-diarrheals, etc.).

CONFIDENTIAL

This document is confidential. Do not disclose or use except as authorized.

All adverse events experienced by participants will be collected from the time of the first dose of study treatment, through the study and until the final study visit. Participants continuing to experience toxicity at the off study visit may be contacted for additional assessments until the toxicity has resolved or is deemed irreversible.

The following guidelines are provided for the modification of dose of ganetespib in the event of toxicities attributed by the investigator to this drug. Toxicities unrelated to ganetespib will not ordinarily result in modification of ganetespib dose.

Once a dose has been reduced, it should not be re-escalated.

Missed doses should be *skipped*, rather than held. Therefore, one cycle will nearly always be 4 weeks, allowing time for vacation, holidays, etc.

CONFIDENTIAL

This document is confidential. Do not disclose or use except as authorized.

Dose Modification Guidelines for Ganetespib

Toxicity	Grade	Guideline for management	Ganetespib dose modification*
Diarrhea	1	See Section 5.5	None

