	2	See Section 5.5	None; If unacceptable to patient or medically concerning despite maximal supportive measures, then skip until recovery to \leq grade 1 (or baseline), up to 21 days*. Restart at same dose**.
	≥ 3		If grade 3 or greater despite maximal supportive measures, skip until recovery to \leq grade 1 (or baseline), up to 21 days*. And then Reduce 1 dose level.
Nausea/vomiting	1 or 2	Treatment as appropriate.	None
	3 (First or 2 nd occurrence)	Treatment as appropriate.	Skip until recovery to \leq grade 1 (or baseline), up to 21 days*. And then Restart at same dose.
	3 (3 rd or more occurrence)		If grade 3 or higher despite optimal prophylactic measures, then skip until recovery to \leq grade 1 (or baseline), up to 21 days*. And then Reduce 1 dose level.
Fatigue	1	No intervention	None
	2	Treatment as appropriate.	None; If unacceptable to patient or medically concerning then hold until recovery to \leq grade 1 (or baseline), up to 21 days*. Restart at same dose**.
	3	Treatment as appropriate.	Skip until recovery to \leq grade 1 (or baseline), up to 21 days*. And then Reduce 1 dose level.
Other non-Hematologic toxicity	1	No Intervention	None
	2	Treatment as appropriate	None; If unacceptable to patient or medically concerning then skip until recovery to \leq grade 1 (or baseline), up to 21 days*. Restart at same dose**.
	2 prolonged or clinically significant and grade ≥ 3	Treatment as appropriate	Skip until recovery to \leq grade 1 (or baseline), up to 21 days And then Reduce 1 dose level*

CONFIDENTIAL

This document is confidential. Do not disclose or use except as authorized.

Toxicity	Grade	Guideline for management	Ganetespiib dose modification*
Infusion reactions	3	Treatment per institutional guidelines for infusion reactions	Contact Principal Investigator to determine whether patient may be retreated
	4	Stop infusion	Permanently discontinue
Thrombocytopenia	1 or 2	No intervention	None
	3	No intervention	Skip until recovery to \leq grade 1 (or baseline), up to 21 days And then Reduce 1 dose level*
Hemoglobin	1 or 2	Treatment as appropriate	None
	3	Treatment as appropriate	Skip until recovery to \leq grade 1 (or baseline), up to 21 days And then Reduce 1 dose level*
Neutropenia	1 or 2	No intervention	None
	3 (ANC < 1,000/ μ L) lasting > 7 days		Skip until recovery to \leq grade 1 (or baseline), up to 21 days And then Reduce 1 dose level*

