Cardiac toxicity	3 (first occurrence of QTc \geq 501 ms on average of triplicate recordings)		Reduce dose level to 120 mg/m ² after the QTc has decreased to at least < 470 ms.
	3 (repeat occurrence of QTc \geq 501 ms on average of triplicate recordings)		Permanently discontinue
	4 (QTc \geq 501 ms or > 60 ms change from baseline and torsades de pointes or polymorphic ventricular tachycardia or signs/symptoms of serious arrhythmia)		Permanently discontinue

* if no recovery after 21 days, patients should go off study

** if dose has been previously held for grade 2 toxicity and grade 2 symptoms recur, OR if the patient finds the symptoms unacceptable, hold dose until recovery to \leq grade 1 and then reduce dose one level

In the case of grade 4 hematologic or non-hematologic toxicity, ganetespiib should be skipped until recovery to grade 1 or less (or baseline), up to 21 days, and then the dose reduced to 150 mg/m². Subjects unable to tolerate ganetespiib at a dose level of 150 mg/m² or whose ganetespiib related toxicity has not returned to baseline or Grade \leq 1 within 21 days should stop ganetespiib. Patients may continue on fulvestrant alone at this time. Once permanently discontinued, ganetespiib should not be restarted.

In the case of a recurrent grade 3 event after prior dose reduction, ganetespiib should be held until the related toxicity has returned to baseline or Grade \leq 1. Subjects should be

CONFIDENTIAL

This document is confidential. Do not disclose or use except as authorized.

reduced by 1 additional dose level (i.e. 2 dose levels from baseline) upon restarting study drug. Only 2 dose reductions are allowed per protocol.

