9. STUDY CALENDAR

All subjects must sign an informed consent document prior to initiation of any study related procedures. The informed consent document must be signed within 30 days before randomization. Baseline laboratory evaluations must be completed within 14 days before randomization. Baseline measurements including scans must be completed within 28 days before randomization. QTc must be documented by 12-lead ECG within 28 days before randomization. In the event that the participant's condition is deteriorating, laboratory evaluations should be repeated within 48 hours prior to initiation of the next cycle of therapy.

CONFIDENTIAL

This document is confidential. Do not disclose or use except as authorized.

All assessments must be performed prior to administration of any study medication. Ganetespib should be administered within ± 3 days of the protocol-specified date, unless otherwise noted. All study assessments should be performed within ± 3 days of the protocol-specified date; however, for study assessments minor deviations in scheduling are allowed to account for holidays, vacations, etc. and will not be considered protocol violations. For patients initially assigned to Arm A, after cross-over to Arm C (fulvestrant + ganetespib), fulvestrant dosing may occur up to ± 7 days in order to allow “synchronization” of the fulvestrant and ganetespib “Day 1”.

Each study cycle should last ~28 days. Doses of ganetespib that are missed for any reason should not be considered “held,” but should be considered “skipped”. For example, if a patient is unable to receive Cycle 3 Day 8 (± 3 days) of treatment for any reason, the dose should be skipped and the patient should proceed on the appropriate calendar date to Cycle 3 Day 15 treatment. The purpose of this rule is to hold the cycle length reasonably constant in order to allow “synchronization” of the fulvestrant and ganetespib cycles (since it is unlikely that fulvestrant will be held for any reason). For the purpose of case report forms (CRF) and protocol charts, for patients receiving both fulvestrant and ganetespib, the cycle number should be assigned according to the ganetespib dosing (i.e., day 1 of the ganetespib cycle is considered day 1 of the cycle to be reported in the CRF). For patients receiving fulvestrant only, day 1 of fulvestrant dosing should be considered day 1 of the cycle.

Four study calendars are provided below:

A) Arm A—fulvestrant alone

B) Arm B—fulvestrant + ganetespib

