10. MEASUREMENT OF EFFECT

Although response is not the primary endpoint of this trial, participants with measurable and/or non-measurable disease will be assessed by RECIST 1.1 criteria. For the purposes of this study, participants should be reevaluated every 8 weeks. In addition to a baseline scan, confirmatory scans and clinical measurements with calipers (if applicable) should also be obtained ≥ 4 weeks following initial documentation of an objective response.

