A maximum of 20% of patients (n=14) on this trial may be entered on the strata for patients with non-measurable but evaluable disease (a category which includes but is not limited to patients with bone-only disease). The primary comparison will not be stratified by type of disease (measurable or non-measurable) because the stratification is being used as a mechanism to limit the number of patients with only non-measurable disease.

Based upon data from the EFECT trial, we further assume that up to 11 patients (15%) may be censored for PFS because of being lost to follow-up or receiving non-protocol anti-cancer therapy before they have progressed or died, and that this probability is not different in the two arms.⁴ To be conservative, we assume that this censoring occurs very close to the time that the patient enters the study, so the effective total sample size will be 60, with 20 patients randomized to fulvestrant alone and 40 patients randomized to fulvestrant + ganetespib.

Assuming that PFS has an exponential distribution, and that the true median PFS on Arm A (fulvestrant alone) is 4.0 months, and that accrual takes 20 months (3.5 patients per month), there will be 80% power to detect a prolongation of true median PFS to 8.0 months in Arm B (fulvestrant + ganetespib), using a one-sided 0.05 log-rank test if the patients are followed for 20 months after accrual ends (so, 40 months after accrual starts). If accrual takes only 15 months (4.5 patients per month) and follow up extends to 22 months after accrual ends, there will also be 80% power. If the true median PFS on the single agent arm is longer than 4 months, the power calculations will still be correct as long as the ratio of medians remains the same (e.g. true medians of 5 and 10 months will have the same power as the true medians of 4 and 8 months, provided that the patients are followed long enough to have the same number of expected PFS events, which is 57).

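### Restaging is written in treatment cycles with no calendar anchor; if ganetespib cycles ever run long, scans come later mainly in Arm B and PFS tilts modestly toward ganetespib

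*Combined protocol and SAP*

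**What the plan says.** **Scan timing.** Section 5.1.10 gives a two-cycle interval, with 8 weeks in brackets, and the window "Imaging can be done +/- 1 week from targeted date but before start of the subsequent cycle". The imaging footnotes in section 9 (Calendars A to D) give two cycles with a 7-day window and no equivalent in weeks. Section 10 counts in weeks only: "participants should be reevaluated every 8 weeks", and 10.1 repeats this.

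**How cycles are counted.** In the introduction to section 9, for patients receiving both drugs, "the cycle number should be assigned according to the ganetespib dosing". The sentence is framed as a rule for case report forms and protocol charts. For patients on fulvestrant alone, the cycle runs from the fulvestrant date, and section 9 notes that fulvestrant is unlikely to be held.

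**Missed ganetespib doses.** Section 6.2.1 says they are skipped: "Therefore, one cycle will nearly always be 4 weeks". Section 9 says the same for doses missed for any reason and gives a stable cycle length as the purpose. Its worked example is a missed Day 8 dose.

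**Other wording in 6.2.1.** The grade 2 fatigue row reads "If unacceptable to patient or medically concerning then hold until recovery to" grade 1 or baseline, with a 21-day limit. The double-asterisk footnote to the same table also uses *hold*. For a recurrent grade 3 event after a dose reduction, ganetespib "should be held until the related toxicity has returned to baseline" or grade 1, with no time limit in that sentence.

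**The concern.** Progression is normally dated at the scan that shows it. If one arm is scanned a few days later than the other at each restaging, its events are recorded later even when the true progression times are the same. The log-rank test works on the order of events, so a small systematic lag can matter when many events cluster around shared scan dates.

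The two arms are on different clocks: fulvestrant dates in Arm A, ganetespib Day 1 in Arm B. Equal timing therefore depends on the skip rule being applied to Day 1 doses, and the *hold* wording leaves room for another reading. Day 1 is a natural point for such a decision. From Cycle 2 on, Calendar B schedules the adverse event evaluation on Day 1 and not on Days 8 or 15, and section 2.1 reports fatigue of any grade in 54% of single-agent patients. That makes a Day 1 hold plausible, but it does not give a rate. The stake is the primary PFS comparison, a one-sided 0.05 test on about 57 events.

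**Working it through.** **1. The plan's own figure.** Section 14.2 states "there will be 80% power to detect a prolongation of true median PFS to 8.0 months in Arm B", "using a one-sided 0.05 log-rank test if the patients are followed for 20 months after accrual ends". The inputs are a median of 4 v 8 months (hazard ratio 0.5), 20 v 40 effective patients, 20 months of accrual and 57 expected events.

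- Expected event fraction per arm, with λ = ln 2 / median, accrual A and further follow-up F: 1 − [exp(−λF) − exp(−λ(A+F))] / (λA). With A = F = 20 this gives 0.991 × 20 = 19.8 events in Arm A and 0.916 × 40 = 36.6 in Arm B, total 56.5. The alternative of 15 + 22 months also gives 56.5.
- Schoenfeld power at 57 events: √(57 × 1/3 × 2/3) × ln 2 − 1.645 = 3.559 × 0.693 − 1.645 = 0.822, so power is 79.4%.

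The stated 80% and 57 events reproduce. This point does not change them.

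**2. Where the two readings part.** Suppose Day 1 of Cycle 2 is held for 7 days. Two cycles then last 35 + 28 = 63 days, while 8 weeks is 56 days. With a 21-day hold, the figures are 49 + 28 = 77 days and 56 days. No section says which date is the target. If the dose is skipped instead, both readings give 56 days.

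**3. Effect on the test when there is no treatment difference.** Simulation set-up: 20 v 40 patients, exponential PFS with equal medians, uniform 20-month accrual, cut-off at 40 months, progression dated at the first scan after the true event, one-sided log-rank at z > 1.645. Scans fall every second 28-day cycle, with or without uniform scatter of ±7 days. Arm B cycles are lengthened at **assumed** rates, because the documents give none.

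False-positive rate, both medians 4 months, 7-day holds:

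| Arm B cycles with a hold | ±7 d scatter (20,000 runs) | ±7 d scatter, repeat (5,000 runs) | No scatter (5,000 runs) |
|---|---|---|---|
| none | 0.061 | 0.065 | 0.058 |
| 5% | 0.072 | 0.071 | 0.070 |
| 10% | 0.082 | 0.076 | 0.080 |
| 20% | 0.091 | 0.092 | 0.083 |

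Monte Carlo standard error is about 0.002 for 20,000 runs and 0.004 for 5,000.

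- Both medians 6 months, with scatter: 0.070, 0.075 and 0.078 for 5%, 10% and 20%.
- Apparent hazard ratio at 20%: 0.92 to 0.94, against 0.98 with equal timing.
- Holds of 7 to 21 days: 0.071 to 0.085 with scatter. Without scatter they give 0.059 to 0.064 (0.061 to 0.067 on repeat), which is close to no change.

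**4. A second parameterization.** Here whole 8-week blocks slip cumulatively in Arm B (4,000 runs, standard error about 0.004). With scatter, the rate is 0.057 with no slip, 0.075 if 10% of blocks slip by 7 days, 0.085 if 25% slip by 7 days, 0.099 if 50% slip by 14 days, and 0.108 if every block slips by 21 days. The null hazard ratio is 0.92 to 0.97, against 0.99. Without scatter the range is 0.065 to 0.186. The values above 0.15 arise only when every Arm B block slips, which is a stress case.

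**5. Attributable part.** Equal timing already gives about 0.06, so the excess over 0.05 is not all due to slipping. For 7-day holds in 5% to 20% of cycles, the added amount is 0.072 − 0.061 = 0.011 to 0.091 − 0.061 = 0.030. If every missed dose is skipped, the added amount is zero.

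**The case against.** The strongest reply is that the plan already closes this path.

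- Section 9 states that a ganetespib dose missed for any reason counts as skipped and not as held. That answers the very word at issue.
- Sections 5.1.7 and 5.1.8 use *held* for a Cycle 2 Day 8 dose that is simply lost: sampling moves to Day 15 and the cycle does not move. *Hold* in 6.2.1 may be loose drafting for the same thing.
- Section 5.1.10 itself gives 8 weeks, section 10 does so twice, and Calendar D has an 8-week column.
- The cycle-labelling sentence concerns forms and charts and does not say that imaging moves with a dose.
- A held Day 8 or Day 15 dose need not move the next Day 1, and the limit at the start of the next cycle is an upper bound on the scan date.

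Most of this stands. Lengthened cycles are not the plan's default, and a reader who infers that PFS is biased toward ganetespib by design goes further than the documents allow. A reader might also infer that slipping is confined to Arm B. Section 5 permits minor schedule changes and interruptions without naming an arm, although fulvestrant may not be voluntarily omitted, so *mainly Arm B* is the most that can be said.

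Three gaps remain. Section 6.2.1 gives two instructions for a missed dose. The dose that defines the cycle, Day 1, has no worked rule. And nothing ranks cycles against weeks: even Calendar D pairs an 8-week column with an imaging footnote counted in cycles.

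**Conclusion.** This is a conditional weakness and not a demonstrated bias. If the skip rule is applied throughout, scan timing is equal between arms and nothing is added. If some Arm B cycles lengthen and scans follow the cycle, the direction is consistent across the simulations: the one-sided test leans toward ganetespib. The size is modest, about 0.07 to 0.09 against about 0.06 for assumed 7-day holds in 5% to 20% of Arm B cycles, and close to no change for longer holds without scatter in scan dates.

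These figures rest on assumed hold rates, on progression being dated at the first scan after the event, and on Arm A staying on schedule. They are ranges and not predictions. It would be wrong to read the point as a fault in the sample size, since the 80% power and 57 events reproduce. Confidence is medium. The change is worth making because it is cheap and removes the dependence altogether.

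**What to change.** - In 5.1.10 and the calendar imaging footnotes that govern primary PFS (Calendars A, B and D), state scan dates as weeks from randomization: 8, 16, 24 and so on, ±7 days, in both arms, regardless of skipped, held or delayed doses. Calendar C starts after the primary PFS event in Arm A, so it does not affect this comparison.
- Remove the link to the start of the subsequent cycle.
- Keep the looser interval after 1 year, expressed in weeks; 5.1.10 already gives it as 8 to 16 weeks.
- The sponsor should reconcile the skip and hold wording in 6.2.1 and section 9, including what happens to a missed Day 1 dose, so that the same event has one meaning. This review takes no position on which dosing rule is right.

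The cost is amendment wording, with no extra scans. The downside is that a scan may occasionally not fall on a treatment visit.

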- i. A bone scan should be done at baseline and at time of cross-over in all patients. Patients with evaluable but non-measurable disease and with bone metastases should also undergo bone scan once every 2 cycles, unless all of the bony disease is encompassed within the area visualized by the restaging CT and/or MRI. Patients with bone only disease will be evaluated for progression but not for objective response. Patients with measurable disease by RECIST 1.1 need not undergo routine bone scans (with the exception of the baseline and time of cross-over scan) unless there is a clinical indication (example: new bone pain). Bone progression is defined as a bone event requiring intervention (e.g. surgery/radiation), the occurrence of a pathologic fracture or the appearance of new lytic lesions or other new bone destruction thought to be related to cancer by X-ray, MRI, or CT scan. Changes in bone scan should not be used to define progression. Disease "hot spots" detected on bone scan should be evaluated radiographically by X-ray, MRI, or CT scan to ascertain the presence of bone destruction versus a healing reaction. The appearance of new lesions on bone scan may constitute progressive disease if associated with clinical symptoms suggestive of disease progression. Patients with bone metastases will also be considered as having progressive disease if there are new and/or progressive lesions in non-bone sites.

CONFIDENTIAL

This document is confidential. Do not disclose or use except as authorized.

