10.1.10 Response Review

The study will use the DF/HCC Tumor Imaging Metrics Core (TIMC) for central protocol measurements. For patients in Arm A, central confirmation of progression including DF/HCC TIMC review and confirmation by the overall study PI is required prior to crossover to Arm C and receipt of ganetespib.

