10.2 Guidelines for Following Patients with Non-Measurable but Evaluable Disease

Patients with non-measurable but evaluable disease will be evaluated for progression but not for objective response. Bone progression is defined as a bone event requiring intervention (e.g., surgery/radiation), the occurrence of a pathologic fracture or the appearance of new lytic lesions or other new bone destruction thought to be related to cancer by X-ray, MRI, or CT scan. *Changes in bone scan alone should not be used to define progression.* Disease "hot spots" detected on bone scan should be evaluated radiographically by X-ray, MRI, or CT scan to ascertain the presence of bone destruction versus a healing reaction. The appearance of new lesions on bone scan may constitute progressive disease if associated with clinical symptoms suggestive of disease progression. In cases of uncertainty, FDG-PET may also be used to provide additional data; however, it should be noted that early "flare" responses may suggest response to therapy rather than progression (Ellis et al, J Am Med Assoc 2009). If a patient with bone-only disease progresses in another organ site per RECIST, that patient will also be counted as progressing.

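### Only Arm A gains ganetespib by progressing, yet the plan neither masks those who confirm progression nor says whose read and date define the PFS event

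*Combined protocol and SAP*

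**What the plan says.** **Arms and crossover.** Section 5 gives fulvestrant injections in Arm A and adds ganetespib infusions in Arm B. No placebo or masking is described. Arm A patients may cross over to the combination once progression is centrally confirmed, and 9.3 expects the first ganetespib dose within two weeks of documented progression. In Arm B, progression ends protocol treatment (5.7, 5.9).

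**Who confirms progression.** The crossover work-up in 5.1.12 lists film review by TIMC and, in the same bullet, "confirmation of progression by overall study PI (REQUIRED before patient receives first dose of ganetespib". Section 10.1.10 repeats for Arm A that "central confirmation of progression including DF/HCC TIMC review and confirmation by the overall study PI is required prior to crossover to Arm C". Section 5.1.13 requires the same two steps in either arm when a patient stops treatment for progression. If the reason is something else, real-time review is not needed, but "central review will be performed at a later time in order to adjudicate the primary endpoint (PFS". Appendix G (1.2) identifies the sponsor as the overall PI, and 11.6 names that PI as IND holder.

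**The endpoint.** Sections 10.1.8 and 14.2 run PFS to progression or death and name no reader. Sections 10.1.4 and 10.1.5 give one dating rule: an equivocal new lesion that is later confirmed takes the date of the scan that first showed it. They do not say whose reading applies. The plan assumes "the true median PFS on Arm A (fulvestrant alone) is 4.0 months" and states that "there will be 80% power to detect a prolongation of true median PFS to 8.0 months in Arm B", "using a one-sided 0.05 log-rank test".

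**Bone scans.** Footnote i, the same in Calendars A and B, says "A bone scan should be done at baseline and at time of cross-over in all patients". It also says that bone-scan change should not define progression, with one exception, repeated in 10.2: "The appearance of new lesions on bone scan may constitute progressive disease if associated with clinical symptoms suggestive of disease progression".

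**The concern.** The trial is open-label in effect, and the consequence of calling progression differs by arm. For an Arm A patient it opens access to the study drug; for an Arm B patient it closes it. Progression also leaves room for judgment: unequivocal worsening of non-target lesions (10.1.5), a bone event needing intervention, or new bone-scan lesions with symptoms (10.2). If borderline findings are called sooner in Arm A, control PFS shortens for a reason unrelated to drug effect, and the error favors ganetespib in a one-sided test.

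Two features make such a call hard to check afterwards. The later adjudication in 5.1.13 is written for patients who stopped for reasons other than progression; for progressions confirmed in real time, no second, independent read is described. And once an Arm A patient has crossed over and the cycle count has restarted, later scans are taken on ganetespib and cannot show whether the call on fulvestrant alone was right.

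**Working it through.** **1. The plan's own figure.** Inputs from 14.2: one-sided α 0.05, medians 4 v 8 months (HR 0.5 under exponential PFS), effective 20 v 40 patients, 57 expected events, 20 months' accrual plus 20 months' follow-up.

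Expected events, with λ = ln 2 / median: P(event) = 1 − [e^(−λ·20) − e^(−λ·40)] / (20λ).
- Arm A, λ = 0.1733: 20 × 0.9913 = 19.83.
- Arm B, λ = 0.0866: 40 × 0.9160 = 36.64.
- Total 56.5, in line with the stated 57.

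Power (Schoenfeld) = Φ(√(57 × 1/3 × 2/3) × ln 2 − 1.645) = Φ(3.559 × 0.6931 − 1.645) = Φ(0.822) = 0.794. A log-rank simulation of the same design gives 0.806. The stated 80% reproduces and the design figures stand.

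**2. Sensitivity to an assessment-only effect.** With no true effect, suppose differential calling alone produces an apparent hazard ratio h. The one-sided error is then Φ(3.559 × |ln h| − 1.645).

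| Assumed h | One-sided error |
|---|---|
| 0.95 | 0.072 |
| 0.90 | 0.102 |
| 0.85 | 0.143 |
| 0.80 | 0.197 |

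**3. Simulation of early calls.** Assumptions: 20 v 40 patients, both medians 4 months, exponential times moved up to the next 8-week scan, 20 + 20 months, no early calls in Arm B. A random share of Arm A progressions is moved one scan earlier, never before the first scan. Rejection means log-rank z beyond 1.645 in favor of Arm B. Two separate runs:

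| Share of Arm A called one scan early | 4,000 trials per setting | 3,000 trials per setting |
|---|---|---|
| 0% | 0.058 | 0.055 |
| 10% | 0.064 | 0.073 |
| 20% | 0.084 | – |
| 25% | – | 0.094 |
| 30% | 0.106 | – |
| 50% | 0.138 | 0.146 |

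Monte Carlo standard errors are about 0.004 to 0.006. The fair comparison is with the simulated 0% row, not with 0.05. At 10% the two runs differ and the increase is small; from 20% upward it is clear. Progressions already at the first scan cannot move. With 8 weeks = 1.84 months they are 1 − e^(−0.1733 × 1.84) = 27% of the total, so the share actually shifted is about 0.73 times the nominal share.

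**4. Bone scan, side by side.**
- At progression or crossover: scheduled in 5.1.12 and in the progression column of Calendar A; absent from 5.1.14 and from the progression column of Calendar B.
- Every two cycles: the same rule in both calendars. Patients with measurable disease are exempt apart from baseline, crossover and clinical indication. By 14.4 that stratum is about 57 of 71 patients, so for most patients the only scheduled post-baseline bone scan before or at first progression belongs to Arm A.
- Calendar D lists an off-study bone scan and covers Arm B patients who have stopped ganetespib.

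**The case against.** The other side has real weight.

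- *A reader might infer that the sponsor-investigator alone decides progression.* The documents do not support that. TIMC review stands in the same bullet as the PI sign-off, and both steps apply in either arm. An early call in Arm A has to pass TIMC as well.
- *A reader might infer that the central read is not used for the endpoint.* Section 5.1.13 says otherwise: central review is required in real time for progressions and is done later for other patients expressly for PFS. What is missing is a masking statement and a rule on whose read and date count.
- *A reader might infer that only Arm A can have a bone scan at progression, and that this scan shortens its PFS.* That is too strong. Bone-scan change alone cannot define progression, and hot spots need X-ray, CT or MRI. The symptom exception is open to both arms, because new bone pain prompts a scan in either, and Calendar D adds scans in Arm B. The crossover scan may also simply serve as the Arm C baseline.
- The incentive for late calls in Arm B is uncertain: ganetespib may be stopped for toxicity, or electively after six cycles, without progression. Arm B also has extra Day 8 and Day 15 visits, which could bring clinical progression to notice sooner.
- TIMC's own procedures are not in these documents, so silence does not prove that its readers know the arm. The plan calls this an exploratory phase II study, for which an open-label design is a legitimate choice.

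What survives: equal procedure is not masking when the consequences differ by arm, and no sentence fixes the source of the PFS event or its date.

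**Conclusion.** The point holds as an omission in the endpoint definition, not as evidence that bias occurred. No masking is stated for TIMC or the PI, the PI is sponsor and IND holder, only Arm A gains ganetespib by progressing, and the PFS sections do not say whose read or date prevails. With about 57 events, modest differential calling matters: nominal one-scan-early calls in 20 to 30% of Arm A progressions take the one-sided error from about 0.055 to about 0.08–0.11, and an apparent HR of 0.90 from assessment alone takes it to about 0.10.

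These sizes rest on assumed rates, on every early call surviving TIMC review, and on none occurring in Arm B. The documents give no rate of early or discordant calls. The bone-scan difference is real on paper but a secondary and weak route. The change is worth making because it is cheap and protects the primary endpoint.

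**What to change.** In 10.1.8, 10.1.10 and 14.2:

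1. State that the primary PFS event and its date come from the TIMC read in both arms, with readers masked to arm. Requests for review should not reveal the arm, and symptoms or bone events should be supplied without arm labels. Deaths count as already defined.
2. State that PI sign-off remains a gate for crossover or stopping treatment but does not set the PFS event or date.
3. State how PFS is handled for an Arm A patient who crosses over without a TIMC-dated progression. The censoring rule in 10.1.8 covers only non-protocol therapy, which Arm C is not.
4. Report site/PI versus TIMC progression by arm, and repeat the PFS analysis on site/PI dates as a sensitivity analysis.

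Separately, reconcile the bone-scan entries of Calendars A and B and of 5.1.12 and 5.1.14, so that the evidence used to adjudicate first progression for PFS is the same in both arms. Excluding the scan from adjudication in Arm A alone would create a new asymmetry.

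Cost: wording, plus removal of arm information from imaging requests; the readers and scans are already in the plan. If retrievable, scans already taken can be re-read masked. The downside is some disagreement between treatment decisions and the analysed PFS date, which items 3 and 4 bring into the open.
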